7.2.5 Recruitment and Study Duration

The following subject status definitions apply:

- Enrolled: A subject that has a signed the Informed Consent form for the study.
- Screen Fail: An Enrolled subject that has been determined to not meet one or more eligibility criteria.
- Participated: Consented subjects who have met all eligibility criteria, have qualified for surgery, and have been randomised.
- Implanted: A participating subject who has received the IMD/comparator in accordance to the randomisation assignment
- Treatment Failure: A participating subject who has not been successfully implanted or does not receive the IMD or comparator treatment in accordance with the randomisation assignment
- Discontinued: An Enrolled subject who withdrew consent, was discontinued by the Investigator or Sponsor before the expected End of Study visit or lost to follow-up. Discontinued subjects may still have safety follow up data collection until their scheduled End of Study visit, for reasons described in section 7.2.6.
- Completed: Enrolled subjects who complete the required treatment and visit schedule.

The recruitment period for the clinical investigation is estimated to be 28 months from the time of first subject consent to recruitment of the last subject. If the recruitment numbers increase following the interim analysis, the recruitment period is expected to extend approximately one month for every eight enrolments.

The expected duration of each subject's participation in the clinical investigation, is 14 months. From the time of implant through to the End-of-Study visit is 12 months after implantation.

Therefore, the anticipated total duration of the clinical investigation is 42 months. Clinical Investigation completion is at the last subject's last visit. In the event of ongoing SAEs/SADEs at the time of a subject's last visit, the subject's clinical investigation completion will be extended for a further 30 days, or until resolution or stabilisation of the event, whichever comes first.

7.2.6 Criteria and Procedures for Subject Withdrawal

Subjects can decide to withdraw from the investigation at any time. The Investigator shall ask the reason(s), however subjects have the right to withhold their reason if preferred. The reason for withdrawal should be documented in the subject's source files and the case report form (CRF), if provided.

The Investigator or Sponsor may also decide to withdraw a subject from the clinical investigation or stop the use of the investigational device if it is considered to be in the subject's best interests.

Subject withdrawal may be for any of the following reasons:

- Adverse Event (AE)
- Device Deficiency (DD)
- CIP or GCP deviation
- Subject withdrew consent
- Subject lost to follow-up

- Subject death
- Sponsor decision
- Investigator decision
- Other (specify): Treatment failure

If subject withdrawal is due to problems related to the IMD and/or comparator safety or performance, the Investigator shall ask for the subject's permission to continue in safety follow up (for example, adverse events and device deficiencies) until their scheduled End-of-Study visit.

If a subject is lost to follow-up, every possible effort must be made by the study site personnel to contact the subject and determine the reason for discontinuation. At least 3 separate attempts taken to contact the subject must be documented.

Participating subjects who are withdrawn/discontinued will not be replaced.

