If the IMD or comparator is inserted but not implanted (eg implanted with commercial device), the subject should remain in the clinical investigation for 30 Days or until all AEs are resolved (whichever is longer).

If the IMD or comparator is implanted and then explanted during Surgery or at a later date, the subject should remain in the clinical investigation for 30 Days or until all AEs are resolved (whichever is longer).

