7.3.3 Safety Evaluations and Procedures

The risks and anticipated ADEs for the CI632D and CI632, as identified in Sections 8.2 and 8.3 of the CIP, will be assessed in the clinical investigation via reporting of all AEs/ADEs from the time of first subject randomisation until last subject last visit. Individual collection of adverse events will end when the subject exits the clinical investigation. Safety data review will be conducted by the Sponsor's Safety Officer in accordance with the Sponsor's standard operating procedures.

Safety data review will be conducted by an Independent Data Monitoring Committee (IDMC) in accordance with the defined Charter for operations.

Upon review of data available in the CRF, the Sponsor or IDMC may query data or request de-identified source documents to review the event.

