9.7. Safety Analyses

Safety analysis will be completed with the AT population at both 6 months and 12 months post-cochlear implantation. The rate of AE type will be compared between treatment and control arm.

For AE/ADEs and DDs, data will be tabled to present event type, severity, device/procedural relationship, count and percentage, and subjects with event will be summarised by randomisation group. Any subjects who died, who discontinued an intervention due to an AE/ADEs, or who experienced a severe or an SAE/SADEs will be summarised separately. In addition to Secondary Endpoint Analyses, AE/ADE and DD frequency data will be provided to the IDMC in accordance to the IDMC Charter.

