11.2. Recording and Handling of Adverse Events

Subjects shall be carefully monitored during the clinical investigation and the investigator should enquire about AEs at investigation visits.

All AEs will be recorded from the time of treatment assignment (randomisation). AE recording will continue for each subject until completion of their End of Study visit. Ongoing SAEs will be followed for 30 days, or until resolution or stabilisation of the event, whichever comes first.

Source notes should indicate the evaluation for AEs, even if there was none to report. All required AEs will be reported if observed, even if anticipated and/or acknowledged as a risk factor in the consent.

All AEs will have the following information documented: start and stop dates, action taken, outcome, severity and investigators opinion on the potential relationship to the IMD and/or comparator and study procedures. If an AE changes in severity, the most severe (highest) grade will be captured for that event on the Adverse Events CRF.

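### Section 7.2.6 requires an offer of continued safety follow-up only after device-related withdrawal, so adverse-event ascertainment stops at exit for others who keep the implant, and Section 11.2 reads differently

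*Protocol*

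**What the plan says.** Section 7.2.6 gives nine withdrawal reasons, introduced by "Subject withdrawal may be for any of the following reasons". They include deviation from the plan or from GCP, withdrawn consent, and Sponsor or Investigator decision. The duty to seek continued safety follow-up covers one class of withdrawal only: "If subject withdrawal is due to problems related to the IMD and/or comparator safety or performance, the Investigator shall ask for the subject's permission". The same section notes that "subjects have the right to withhold their reason if preferred".

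Three other sections bear on when collection ends:

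- Section 7.2.5, in its definition of a discontinued subject: "Discontinued subjects may still have safety follow up data collection until their scheduled End of Study visit, for reasons described in section 7.2.6". This is permissive and points back to the condition in 7.2.6.
- Section 7.3.3: "Individual collection of adverse events will end when the subject exits the clinical investigation".
- Section 11.2: "AE recording will continue for each subject until completion of their End of Study visit".

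On the analysis side, Section 9.7 states: "Safety analysis will be completed with the AT population at both 6 months and 12 months post-cochlear implantation". Section 9.5 defines the As-Treated set by receipt of a CI632 or CI632D, with no condition on completing follow-up.

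**The concern.** The subjects at issue withdraw for a reason not attributed to the device but keep the implant. Nothing prescribes adverse-event collection for them after exit, although they remain exposed and remain in the analysis set. Whether they are followed depends on a cause perceived at the moment of withdrawal. Subjects may withhold that reason, and a later event need not be connected with it.

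At stake is secondary endpoint 1, the comparison of procedural and device-related adverse events at 6 and 12 months, which serves the secondary objective of showing similar safety. Section 8.4 relies on the IDMC reviewing infection-related events throughout the study, and the IDMC can review only what is collected. This is a data-collection rule, so no method in the SAP could recover events that were never recorded.

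**Working it through.** **Reading the sections together.** For a subject who withdraws with the implant still in place:

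| Section | Adverse-event collection after withdrawal |
|---|---|
| 7.2.6 | Must be offered if the reason is device safety or performance; silent for other reasons |
| 7.2.5 | Possible, for the reasons in 7.2.6 |
| 7.3.3 | Ends at exit |
| 11.2 | Continues for each subject to the End of Study visit |

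Sections 7.2.5, 7.2.6 and 7.3.3 together leave no prescribed collection after a non-device withdrawal. Section 11.2 conflicts with this on its face. It does not say whether a withdrawn subject's End of Study visit is the scheduled one or an early one at exit, so it does not clearly close the gap. By contrast, Section 7.3.2.7.3 has its own rule for subjects whose device was not finally implanted or was explanted: they stay at least 30 days, longer if adverse events are unresolved, whatever the cause. No equivalent covers subjects who leave with the device in place.

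**Size. Inputs:** up to 60 subjects per arm (Section 7.1) and attrition of approximately 10% (Section 9.4). The gap itself rests on no stated figure. The attrition allowance belongs to the sample size for impedance, and that calculation reproduces: a difference of 1.5 kOhm, SD 2.0, one-sided alpha 0.025 and power 0.9 give 38.35 by the two-sample t-test, rounded up to the stated 39 per arm (power 0.905).

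1. Withdrawals = N × attrition = 60 × 0.10 = 6 per arm, or 12 in total, for all reasons.
2. Share of 12-month observation time lost = attrition × mean fraction of follow-up remaining. With withdrawals spread evenly over 12 months and nobody followed afterwards: 0.10 × 0.5 = 5%. If all leave straight after surgery: 0.10 × 1 = 10%.
3. For assumed attrition of 5% to 15%: 60 × 0.05 = 3 to 60 × 0.15 = 9 per arm, and 2.5% to 7.5% of observation time under even withdrawal.
4. Chance of seeing at least one event in an arm of 60 = 1 − (1 − p)^60. Here p is an assumed true 12-month risk, multiplied by 0.95 (even withdrawal) or 0.90 (ceiling):

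| Assumed risk p | Full follow-up | 5% of time lost | 10% of time lost |
|---|---|---|---|
| 2% | 0.702 | 0.684 | 0.664 |
| 5% | 0.954 | 0.946 | 0.937 |

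5. One missed event changes an arm's rate by 1/60 = 1.7 percentage points.

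**The case against.** The strongest reply is that Section 7.2.6 obliges the Investigator to ask one group and does not forbid asking others, while Section 11.2 already provides for recording in every subject. The first half is correct: this is an absent duty, not a prohibition. The second half is only partly an answer, because Section 11.2 conflicts with Section 7.3.3 and leaves open which visit it means.

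The second reply is that much of the attrition is beyond repair. Death and loss to follow-up gain nothing from an offer, and withdrawn consent needs fresh permission. Device-related problems already fall within the condition, and explants have their own rule. The 10% was set for a 6-month impedance endpoint and may include randomised subjects never implanted, who are outside the As-Treated set. All of this stands. It makes the avoidable part smaller than the figures above.

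Four stronger readings might tempt a reader, and the documents do not support them.

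- *These subjects fall out of the safety comparison.* They do not. The As-Treated set keeps everyone who received a device, events before exit count, and someone who leaves after month 6 loses nothing at 6 months.
- *They are counted as event-free after exit.* Section 9.7 does not say how partial follow-up enters the rates. That is a matter for the SAP, which is not at hand.
- *The comparison between arms is biased.* The rule is the same in both arms, and subjects and the investigators assessing adverse events are blinded (Section 7.2.7.1). Follow-up chosen by perceived cause could differ by arm, but nothing shows that it does. The unblinded Sponsor's power to withdraw a subject is tied in Section 7.2.6 to the subject's best interests, and nothing suggests another use.
- *Late infection, the high-rated risk, would go unseen.* Section 8.3.1 does not speak of late infection. It gives a remote likelihood, and the rating follows from the severity category.

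**Conclusion.** The point holds in limited form. The only stated duty to offer continued safety follow-up depends on a device-related reason for withdrawal, and the sections disagree on when collection ends. The consequence is truncated ascertainment after exit in subjects who remain in the safety set and carry the device.

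The effect is modest: about 5% of 12-month observation time per arm, 10% at most, with only part of it avoidable. This rests on the protocol's approximately 10% attrition carrying over to 12 months, withdrawals spread evenly, no follow-up after exit, and event risk roughly constant over the year. Section 9.3.2 plans no error-controlled test for the secondary endpoints, so no formal conclusion depends on this. The change is still worth making, because it is cheap and the lost data cannot be recovered at analysis.

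**What to change.** In Section 7.2.6, remove the causal condition. For any withdrawn or discontinued subject who retains the CI632D or CI632, whatever the reason, the Investigator asks permission to go on collecting adverse events and device deficiencies to the scheduled End-of-Study visit. The subject may refuse, and the answer is recorded.

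Then reconcile three sections so that they give one end point for adverse-event collection: the discontinued definition in 7.2.5, the exit rule in 7.3.3, and the recording period in 11.2. One consistent wording would be the scheduled End-of-Study visit, or the date on which the subject declines further safety contact if earlier. The rule in 7.3.2.7.3 for devices not implanted or explanted can stay as it is.

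The cost is protocol and consent wording plus a few safety contacts for about a dozen subjects at most (10% of 120).

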7.2.7 Randomisation Procedures

Subjects who meet all eligibility criteria with approval by an independent Sponsor representative, will be randomised to an intervention based on a computer-generated randomisation schedule prepared by a Statistician. Subjects will be randomly assigned to one of two interventions using a ratio of 1:1 within each site. Assignment to intervention groups will be determined by a system defined under a randomization plan. The investigational medical device or comparators will be packaged and labelled for blinded randomization.

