6.3 Exploratory Objective

7 DESIGN OF THE CLINICAL INVESTIGATION

7.1 General

Figure 7: Schematic for study.

The clinical investigation is a pivotal, prospective, multi-centre, randomised, blinded, two-arm, parallel, comparator-controlled trial in an adult population with post-lingual, bilateral, moderate to profound sensorineural hearing loss.

Clinical investigation subjects include adults (age ≥ 18 years old) with post-lingual, bilateral, moderate to profound sensorineural hearing loss at 5-25 clinical investigation sites in Australia, New Zealand, and United States. Eligibility criteria includes assurance subjects are able to participate in either arm of the trial, present with similar profiles to current device indications, and able and willing to complete the clinical investigation. Potential subjects will be formally consented to participate in the clinical investigation and all eligibility criteria confirmed prior to 1:1 randomisation into one of two arms: implantation with CI632D IMD or CI632 comparator device.

Randomised subjects cannot be replaced and will count toward the total trial population. Up to 60 subjects will be randomised into each arm for a combined total of up to 120 randomised subjects. A group sequential analysis will be completed which may impact the final number of subjects.

To limit bias during data collection, the subject and clinicians completing questionnaires and speech perception testing will be blinded to the randomisation assignment, see Section 7.2.7. The implanting surgeon will not be blinded to the randomisation assignment.

The primary endpoints assess the efficacy of the IMD by measure of impedance and speech perception of words in quiet. Secondary endpoints include efficacy assessment via sound processor battery life estimation and safety assessment via adverse event collection and speech perception performance tested in specified listening conditions. Data collection for endpoint assessment and all other clinical investigation measures are listed in the Schedule of Events.

The Sponsor's data monitoring requirements are summarised in Section 22.1 and described in detail in a separate Monitoring Plan. An Independent Data Monitoring Committee (IDMC) will be used for safety and compliance oversight. Activities of the IDMC are documented in the IDMC Charter.

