7.2.7.1 Blinding Procedures

The clinical investigation is partially blinded, with the subject and delegated site personnel who will administer tests and subject facing questionnaires and program the device being blinded to the treatment assignment. This is to reduce risk of bias during these assessments. Training to blinding and unblinding procedures will be provided prior to site personnel prior to them completing clinical investigation activities. Where required for resourcing reasons, prior approval may be sought from the Sponsor for site personnel to be blinded to the subjects they will test, but not the subjects they will not test.

IMD and comparator packaging will be visually identical with exception of tracking numbers that will not identify the device type.

Investigators performing the cochlear implant surgery will not be blinded to the randomisation assignment. Blinding the surgeon is not possible as there are visually apparent differences between the two devices. Surgeons and other unblinded site personnel will be instructed to not disclose randomisation assignment through discussion, documentation or other means. The surgeon will be instructed to document the "cochlear implant" (or similar) was implanted in medical records. The monitor will need to ensure blinded site personnel do not become unblinded during discussions.

The Data Management Plan includes processes for managing the randomisation process. The Sponsor will not be blinded to the randomisation assignment. The Sponsor's delegated monitor(s) will be blinded to the randomisation assignment.

Investigators completing adverse event assessments will be blinded to the randomisation assignment. The IDMC will be aware which randomisation group a subject is randomised, but identification of the group (Cl632 or Cl632D) will not be provided to the IDMC. The Sponsor will only analyse data as outlined in this clinical investigation plan. The Sponsor will provide data to the IDMC as outlined in the IDMC Charter and as requested; the Sponsor will not evaluate this data.

At the end of the clinical investigation, the database will be locked. After this time point, subjects and blinded site-personnel may be unblinded to the randomisation assignment and subjects' medical records may be updated.

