9.4. Sample Size Determination

The following evidence was used to support the sample size calculation of the first primary endpoint:

Cochlear[™]'s feasibility clinical investigation CLTD5495 comparing outcomes of the dexamethasone eluting Cl400 Combined Investigational Device (Cl4CID) and standard Cl24RE(CA) device. At 6 months post-activation MP1+2 impedance data showed a decrease of 3.8 kOhms for the Cl4CID compared to the Cl24RE(CA). The Cl4CID standard deviation from its mean was 1.0 while the Cl24RE(CA) standard deviation was 1.7. The electrode array used in this clinical investigation is the Contour Advance electrode.

CI632 predicate device is the Cochlear[™] Nucleus[®] CI532 cochlear implant with Slim Modiolar electrode (CI532). Six month mean MP1+2 impedance data for 43 subjects under the clinical investigation CLTD5446 provides similar results to the CI24RE(CA) control group of the CLTD5495 clinical investigation, with mean MP1+2 impedance measuring at 7.9 kOhms with a standard deviation of 1.7.

Considering results from CLTD5495 and CLTD5446, the following assumptions have been made regarding this clinical investigation:

Using an independent t-test (SigmaPlot 13.0) the sample size has been calculated to have reasonable power to detect a 1.5 kOhm decrease difference in MP1+2 impedance at 6 months post-cochlear implant for those implanted with the CI632D IMD compared to those implanted with the CI632 comparator device.

This change of 1.5 kOhms to be detected is based on clinical consensus and has taken into consideration the significant mean impedance reduction (3.8 kOhms) observed in the CI4CID feasibility clinical investigation CLTD5495. Due to the nature behind the design of CI632, it is likely there will be less insertion trauma as it is a precurved electrode designed to stay closer to the medial wall of the cochlea.

An expected standard deviation (SD) of the change is 2.0 kOhms. This SD of the change to be detected is based on the SD of the mean impedance of 1.7 observed in separate clinical investigations for CI24RE(CA) and CI532. The expected standard deviation of the mean in the current study has been chosen to be more conservative, allowing for increased impedance variability between the two arms.

A significance level α = 0.025 (one-tailed).

A desired power of 0.9

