The sample size for a 1:1 allocation has been calculated to have reasonable power to detect a decrease in mean (SD) MP1+2 impedance of 1.5 kOhm (1.5) for the CI632D IMD compared to the CI632 comparator device at 6 months post-implantation.

A 1.5 kOhms drop in impedance is expected to result in a mean increase in battery life of 1.79 hours for recipients with high powered maps, demonstrating a meaningful clinical benefit. This calculation is based on prior investigation using the DEE battery model (D1672865).

In the absence of literature to support a clinically meaningful change in impedance values for cochlear implants, the Sponsor positions 1.5kOhms effect size as clinically meaningful as shown by the battery life model increasing battery life by a mean of 1.79 hours. An improvement of 1.79 hours in battery life clearly equates to a meaningful duration of time for a cochlear implant recipient, such as a round trip commute to work, multiple meetings at work, a child's soccer game, meal out with friends, etc. The clinical investigation is powered to capture the 1.5kOhm effect size.

Based on these assumptions, a minimum sample size of 39 subjects in both arms is required to reject the null hypothesis of equivalent or higher MP1+2 impedance for the Cl632D IMD compared to the Cl632 comparator device at 6 months post-implantation with a power > 0.9. An increased sample size of 100 subjects (approximately 50 subjects in each arm) will be included, which will allow for the possibility of non-normally distributed data (approximately 15%) and subject attrition (approximately 10%). In addition, the population is extended to 120 randomised subjects to account for uncertainty in the estimates used in the power calculation, with approximately 60 subjects in each arm.

The following evidence and assumpters were used to support the same size calculation of the second primary endpoint:

CI632 predicate device is the Cochlear[™] Nucleus[®] CI532 cochlear implant with Slim Modiolar electrode (CI532). Six month mean CNC word in quiet data 96 subjects under the clinical investigation CLTD5685 provided a mean change of 46 ± 22.6 (SD) word improvement from baseline

A significance α = 0.025 (one-tailed).

A desired power of 0.9

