9.6. Endpoint Analyses

9.6.1. Primary Endpoint Analyses

There are two primary endpoints.

Primary analysis of MP1+2 impedances will include the ITT population evaluating mean differences at 6 months post-cochlear implantation based on a t-test at the one-sided 0.025 alpha level. If there is evidence of non-normality (based on a Shapiro-Wilks test at the 0.05 alpha level), a non-parametric alternative will be employed for the primary endpoint.

Primary analysis of speech perception performance will include the cohort of subjects randomised to CI632D and for whom CI632D is their first cochlear implant in the ITT population, evaluating the difference at 6 months post-cochlear implantation compared to baseline via a one-sample sample t-test at the one-sided 0.025 alpha level. If there is evidence of non-normality (based on a Shapiro-Wilks test at the 0.05 alpha level), a non-parametric alternative will be employed for the primary endpoint.

For both endpoints, analysis may include description of population differences in the final analysis. Additional analysis may include both the AS and PP analyses groups. Missing data will be analysed under a multiple imputation strategy that will be outlined in the Statistical Analysis Plan (SAP).

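### Randomisation is 1:1 within each site, but the primary MP1+2 t-test has no site term: valid and adequately powered, though a site term would be a cheap gain at the early looks if allocation is blocked

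*Protocol*

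**What the plan says.** Section 7.2.7 makes site the unit within which treatment is allocated: "Subjects will be randomly assigned to one of two interventions using a ratio of 1:1 within each site". It does not say whether allocation is in blocks: "Assignment to intervention groups will be determined by a system defined under a randomization plan". Section 7.1 expects "5-25 clinical investigation sites in Australia, New Zealand, and United States".

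Section 9.6.1 fixes the primary MP1+2 analysis in the ITT population as "evaluating mean differences at 6 months post-cochlear implantation based on a t-test at the one-sided 0.025 alpha level", with a non-parametric alternative if a normality test fails. For this endpoint it leaves the multiple imputation strategy to the SAP, but it names the test itself. Site appears in section 9.9 only, as a possible subgroup.

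Section 9.4 sizes the trial with an independent t-test. The effect is 1.5 kOhm, the power 0.9 and the one-sided alpha 0.025, and "An expected standard deviation (SD) of the change is 2.0 kOhms". It allows about 10% for attrition. Sections 9.4 and 9.8 set looks at 50, 80, 100 and 120 randomised subjects with O'Brien-Fleming-like spending. Section 9.8 adds that a group sequential result may support a premarket application if both primary nulls are rejected.

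**The concern.** When a factor is balanced by design and is related to the outcome, an analysis that ignores it overstates the standard error. Balance within site removes the between-site component from the true variance of the treatment difference, but the pooled SD in a plain t-test still contains it. The test then rejects too seldom under the null and loses power under the alternative.

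Sites in three countries, with different surgeons, could plausibly differ in mean impedance, although the protocol gives no figure. What is at stake is the chance of success at the N=50 and N=80 looks, where the boundary is strict and power is not yet near its ceiling.

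**Working it through.** **1. The plan's own figure.** Effect 1.5 kOhm, SD 2.0, one-sided 0.025, noncentral t with noncentrality 1.5 / (2.0 × √(2/n)).
- n = 38 per arm: power 0.897.
- n = 39 per arm: noncentrality 3.312, 76 df, critical value 1.992, power 0.905.

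So 39 per arm is reproduced. (The SD of 1.5 that 9.4 also mentions gives 22 per arm by the normal approximation, so 2.0 is the value behind the 39.)

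**2. Fixed-sample test at N=80.** Assume ICC 0.1 with the total SD held at 2.0. The within-site SD is then 2.0 × √0.9 = 1.897. At 40 per arm the noncentrality is 3.354 and the critical value 1.991.
- Nominal t-test, ignoring the blocking: 91.2%.
- t-test under blocked allocation: Φ((3.354 − 1.991) / √0.9) = Φ(1.437) = 92.5%. Its one-sided error is about Φ(−1.96 / √0.9) = 0.019, so it is conservative.
- Site-adjusted test: noncentrality 3.354 / √0.9 = 3.536, with df reduced for 5, 10 or 25 sites: 93.7%, 93.6%, 93.5%.

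The gap is 1.0 to 1.2 points. It is 0.3 to 0.6 at ICC 0.05 and 2.1 to 2.3 at ICC 0.2. At N=120 and ICC 0.1 it is about 0.3 (98.8% versus 99.0%).

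**3. The sequential design, large-sample.** Cumulative spending 2 × (1 − Φ(2.241 / √t)) at t = 50/120, 80/120, 100/120 and 1 gives 0.0005, 0.0060, 0.0141 and 0.025. The z bounds are 3.28, 2.52, 2.25 and 2.04. With no attrition, blocked allocation and ICC 0.1, cumulative power by N=80 is 81.1% (t-test) versus 84.6% (adjusted), a gap of 3.5 points. By N=120 it is 98.6% versus 99.0%, a gap of about 0.4.

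**4. Simulation of the sequential design.** Assumed: blocks of 4, unequal sites, 10% missing completely at random, 20,000 runs per scenario. The model has a random site intercept with Kenward-Roger correction. Cumulative power (%) at ICC 0.1, t-test versus model:

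| Sites | N=50 | N=80 | N=120 |
|---|---|---|---|
| 5 | 18.4 vs 21.0 | 74.2 vs 77.2 | 97.4 vs 97.9 |
| 10 | 18.0 vs 20.6 | 73.8 vs 76.9 | 97.3 vs 97.9 |
| 15 | 17.4 vs 19.7 | 73.5 vs 76.7 | 97.2 vs 97.7 |
| 25 | 17.2 vs 19.0 | 72.6 vs 75.4 | 97.3 vs 97.7 |

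A separate simulation under the same main assumptions gave 73.7% versus 77.2% (5 sites) and 75.8% versus 78.3% (25 sites) at N=80, with gaps of 0.3 to 0.7 points at N=120. With 20 imputations combined by Rubin's rules, the N=80 gap at the single-look bound was 2.5 to 3.0 points.

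**5. Sensitivity to the unknowns.** Gain at N=80 over the assumed ICC, blocked: 0 to 0.3 points (ICC 0), 1.3 to 1.6 (0.05), 2.8 to 3.2 (0.1), 6.2 to 6.9 (0.2). At N=120 it is 0.7 to 1.0 at ICC 0.2. Overall one-sided error of the t-test is 0.0255 to 0.027 at ICC 0 (Monte Carlo SE 0.0011) and 0.0195 to 0.023 at ICC 0.1. For the model it is 0.024 to 0.0275 over all blocked scenarios.

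Without blocking (5 and 25 sites), the model loses 1.8 to 2.2 points at N=50 and N=80 at ICC 0. At ICC 0.1 and N=80 it gains only 0.1 to 1.4.

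**The case against.** The strongest case against is that nothing here is wrong. The sample size assumes a t-test, the analysis is that t-test, and the power claim reproduces. The gain rests on blocking and on a between-site variance, and the protocol gives neither. If allocation turns out to be unblocked, the plan may already be the better choice. All of that stands, and it is why the severity is low and the fix conditional.

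The practical effect is also small. At ICC 0.1 the expected number analysed at stopping falls by 1.3 to 1.7 subjects (for example 81.3 to 79.7 with 5 sites). Section 7.2.3 lets enrolment continue during the looks. At 120 subjects in 28 months (about 4.3 a month), about 26 more are randomised during the 80th subject's six-month follow-up.

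Three stronger readings are tempting, and the document does not support them:
- A reader might infer that the test is invalid or the trial too small. Both are contradicted by steps 1 and 2.
- A reader might take about 3 points as the power the trial loses. It is cumulative power at one interim look; by N=120 almost all of the gap has closed.
- A reader might take the sentence "The Sponsor will only analyse data as outlined in this clinical investigation plan" in 7.2.7.1 as barring a site term from the SAP. It stands under blinding procedures, beside statements on the unblinded sponsor, while 9.1 and 9.5 send analysis detail to the SAP. It does not by itself force the change into the protocol.

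What survives is that 9.6.1 states the test rather than leaving it open, so revising that stated rule is a fair suggestion and not a complaint about missing SAP detail.

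**Conclusion.** The point holds as a cheap, optional improvement. The primary t-test is valid, supports 39 per arm and keeps its planned power. It becomes conservative only if allocation is blocked within site and sites differ. At an assumed ICC of 0.1 with blocking, it then forgoes about 2.5 to 3.5 points of cumulative power at the N=80 look, about 1 point in a fixed-sample test of that size, and under 1 point by N=120. At ICC 0 there is essentially nothing to gain. The ICC (range 0 to 0.2), the blocks of 4 and the site sizes are assumptions. The SD, effect, attrition and looks are the protocol's.

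**What to change.** Before the first look, check in the randomization plan whether allocation is blocked within site, then amend 9.6.1 and carry the wording into the SAP.
- **If blocked:** make the primary MP1+2 analysis a linear mixed model with treatment and a random site intercept, with Kenward-Roger correction. Use it identically at every look and within each imputed data set, and keep the unadjusted t-test as a sensitivity analysis. Use a random rather than a fixed site effect: with 25 sites at N=80, fixed effects gave 91.4% against 91.8% for the t-test in a fixed-sample simulation.
- **If not blocked:** the t-test may stay.

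The cost is a short amendment, with the agreement and notifications that section 18 requires, and a slightly more complex model. Because section 7.2.7.1 leaves the sponsor unblinded, the change should be documented as made before any outcome comparison by arm. There is no gain if sites do not differ. If the model is used when allocation is unblocked and sites barely differ, it loses up to about 2 points at the early looks.
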